### 21.5.6 End of Study (Day $99 \pm 3$ days)

The following assessments will be performed at the end of study visit:

- Body weight
- Record concomitant medications
- Serum pregnancy test (for females of childbearing potential only)
- Record AEs
- Full physical examination
- Vital signs
- 12-lead ECG (single)
- Clinical laboratory tests (haematology, serum chemistry, coagulation and urinalysis)
- Blood sample for PK
- Blood sample for ADA/nAb

# 21.5.7 Early Termination Visit

The following procedures will be performed if a participant terminates from the study prior to the end of study visit:

- Body weight
- Record concomitant medications
- Serum pregnancy test (for females of childbearing potential only)
- Record AEs
- Full physical examination
- Vital signs
- 12-lead ECG (single)
- Clinical laboratory tests (haematology, serum chemistry, coagulation and urinalysis)
- Injection site reaction assessment (if participant withdraws/is withdrawn prior to Day 6 only)
- Blood sample for PK
- Blood sample for ADA/nAb

#### **List of Abbreviations**

Abbreviation	Description
ADA	Anti-drug Antibody
ADR	Adverse Drug Reaction
AEs	Adverse Events
ALP	Alkaline Phosphatase
ALT	Alanine Aminotransferase
aPTT	Activated Partial Thromboplastin Time
AST	Aspartate Aminotransferase
ATC	Anatomical Therapeutic Class
AUC0-inf	Area Under the Concentration-Time Curve From 0 to Infinity
AUC0-last	Area Under the Concentration-Time Curve From 0 to Time of Last Quantifiable Concentration
BLQ	Below The Limit of Quantifiable
BMI	Body Mass Index
CL/F	Total Apparent Body Clearance
Cmax	Maximum Observed Concentration
CS	Clinically Significant
CSR	Clinical Study Report
CV	Coefficient of Variation
DBP	Diastolic Blood Pressure
ECG	Electrocardiogram
eCRFs	Electronic Case Report Forms
GCP	Good Clinical Practice
GGT	Gamma Glutamyl Transferase
HDL	High-Density Lipoprotein
IAS	Immunogenicity Analysis Set
ID	Identification
IM	Intramuscular Injection
INR	International Normalized Ratio
LDH	Lactate Dehydrogenase
LDL	Low-Density Lipoprotein
MedDRA	Medical Dictionary for Regulatory Activities
NCS	Not Clinically Significant
РК	Pharmacokinetics
PKS	Pharmacokinetic Analysis Set
РТ	Preferred Terms
РТ	Prothrombin Time
SAEs	Serious Adverse Events
SAP	Statistical Analysis Plan
SBP	Systolic Blood Pressure
SD	Standard Deviation
SOC	System Organ Class
SOPs	Standard Operating Procedures
CONFIDENTIAL	Page 5 of 39

SS	Safety Analysis Set
t1/2	Apparent Terminal Elimination Half-Life
TEAEs	Treatment Emergent Adverse Events
TFLs	Tables, Listings, And Figures
Tmax	Time To Cmax
TT	Thrombin time
UN	Unknown
Vz/F	Apparent Volume of Distribution
WBC	White Blood Cells
WHO-DD	World Health Organization Drug Dictionary
λz	Terminal Elimination Rate Constant

## 1 INTRODUCTION

This Statistical Analysis Plan (SAP) provides the outline for the statistical analysis of the data collected for MB05-A-01-21 titled: "FANTASY–A Randomised, Double-Blind, 3-arm Parallel Study to Compare the Pharmacokinetics, Safety, Immunogenicity and Tolerability of MB05 (Proposed Palivizumab Biosimilar), EU-sourced Synagis® and US-sourced Synagis®, Administered as a Single Dose Intramuscular Injection in Healthy Volunteers." (Version 2.0 dated 07 June 2022).

This SAP is written with consideration of the recommendations outlined in the International Council for Harmonisation (ICH) E9 guideline entitled, "Guidance for Industry: Statistical Principles for Clinical Trials" and the ICH E3 guideline entitled, "Guidance for Industry: Structure and Content of Clinical Study Reports.

The SAP will be finalized prior to database lock. Any deviations from the SAP after database lock, reasons for such deviations, and all alternatives or additional statistical analyses that may be performed will be described the Clinical Study Report (CSR).

If the SAP differs the statistical considerations in the protocol, details will be given in section 18.

#### **Summary of Changes**

Statistical analysis plan version 1.0 was approved and executed on 29-Nov-2022. This SAP Version 2.0, 15-Jun-2023 was prepared to include a pharmacokinetic (PK) sensitivity analysis and to remove the analysis of neutralising antibody assessments from the analysis plan following sponsor confirmation that this test will no longer be performed. Section 5.2 pharmacokinetic analysis set definition was updated to add the criteria to include subjects "who received any amount of study treatment". Section 14.8 was updated to include listings and summaries of body mass index (BMI). Additionally, the lead statistician for this study has changed to [name], and the PK signatory is [name], and the sponsor medical monitor has changed to [name]. Avance Clinical's address was also updated.

## **2 PROJECT OVERVIEW**

## 2.1 Description of Study Design

This is a multicentre, randomised, double-blind, 3-arm parallel group study.

Up to a total of 141 participants are planned to be enrolled and randomised to receive a single dose of MB05, EU-Synagis® or US-Synagis with participants randomised to Arm A, B or C in equal proportions (1:1:1). Participants will be enrolled across multiple sites in Australia and New Zealand.

In Group 1, a total of 9 participants will be enrolled and dosed with 3 mg/kg MB05, 3 mg/kg EU-Synagis® or 3 mg/kg US-Synagis® (1:1:1). Once all participants in Group 1 have completed the Day 8 visit, a safety review committee (SRC) will meet to review all available safety data from Group 1, up to and including Day 8. No additional enrolment or dosing of the remaining participants should occur until the safety review is complete.

Following approval by the SRC, Group 2 may be enrolled (n=132, randomised 1:1:1 MB05: EU-Synagis®: US-Synagis®).

#### 2.2 **Objectives**

#### 2.2.1 **Primary Objectives and Endpoints**

#### The primary objective of this study is:

- To establish the bioequivalence between MB05 and EU-Synagis®, between MB05 and US-Synagis® and between EU-Synagis® and US-Synagis® up to Day 99, in terms of:
  - Area under the serum concentration versus time curve from time zero to infinity (AUC0-inf)
  - Maximum observed serum concentration (Cmax)

#### The primary endpoint of this study is:

• Bioequivalence between MB05 and EU-Synagis®, between MB05 and US-Synagis® and between EU-Synagis® and US-Synagis® will be determined for AUC0-inf and Cmax

#### 2.2.2 Secondary Objectives and Endpoints

#### The secondary objectives of this study are:

- To compare the pharmacokinetics (PK) of MB05 with EU- Synagis® and US-Synagis® following a single 3 mg/kg intramuscular injection (IM) injection in healthy adult volunteers.
- To assess the safety and tolerability of MB05, EU- Synagis® and US-Synagis®
- To assess the immunogenicity of MB05, EU- Synagis® and US-Synagis®

#### The secondary endpoints of this study are:

- Additional PK parameters to be determined include (but are no limited to):
  - Time to  $C_{max}(T_{max})$
  - Apparent terminal elimination half-life  $(t_{1/2})$
  - Apparent total serum clearance (CL/F)
  - Apparent volume of distribution (Vz/F)

- $\circ$  Area under the concentration-time curve from 0 to time of time t (AUCt)
- Safety and tolerability endpoints include:
  - Incidence, type, and severity of Adverse events (AEs)
  - Changes from baseline in clinical laboratory results (haematology, serum chemistry, coagulation, and urinalysis)
  - Changes from baseline in vital signs parameters
  - Changes from baseline in physical examination findings
  - Change from baseline in body weight
  - Change from baseline in ECG parameters
  - Incidence, type and severity of injection site reactions
- Immunogenicity endpoints include:
  - Incidence of anti-drug antibody (ADA) against MB05, US- and EU-Synagis®, including titres for ADA

## **3** SAMPLE SIZE

Up to a total number of 141 healthy subjects (male and female) are planned to be enrolled in the study. Subjects who meet the entry criteria will be randomised to receive a single dose of MB05, EU-sourced Synagis® or US-sourced Synagis® in a 1:1:1 fashion.

The reported coefficients of variation (CVs) for AUC and Cmax for Synagis® vary between 0.25 and 0.35. Based on a worst-case CV of 0.35 (Robbie et al., 2012), alpha of 0.05 (i.e., utilising a two-sided 90% CI around the mean difference) and a true hypothesised ratio for the mean difference of 1, a total of 135 subjects (45 subjects per arm respectively), 1:1:1 ratio) will provide approximately 85% power to demonstrate bioequivalence of MB05 with EU-sourced Synagis® and US-sourced Synagis®. Assuming a 5% dropout, a total of 141 subjects (47 subjects per arm) are sufficient for this measure.

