# 13.6.2 Serum Pharmacokinetic Parameters and Bioequivalence Analysis

Serum palivizumab concentrations from samples collected at specific timepoints following IM administration of each study treatment will be used to calculate PK parameters using non-

compartmental analysis methods. The following PK parameters will be determined:

- Cmax Maximum observed serum concentration obtained directly from the concentration versus time data.
- Tmax Time to maximum observed concentration, taken directly from the data. If the maximum serum concentration occurs at more than one time point, the first is chosen.
- kel Terminal elimination rate constant obtained from the slope of the line, fitted by linear least squares regression through the terminal points of the logarithmic concentration-time profiles.
- AUCt Area under the serum concentration-time curve from time zero to time t
- $t_{\frac{1}{2}}$  Apparent terminal half-life, calculated as  $t_{\frac{1}{2}} = \ln (2)/k_{el}$ .
- CL/F Apparent total serum clearance of drug after IM administration, where F is the fraction of drug absorbed, calculated as (Dose / AUC0-inf).
- $\label{eq:Vz/F} Vz/F \qquad \mbox{Apparent volume of distribution during terminal phase after IM} \\ administration, calculated as (CL/F / k_{el}).$

PK parameters for each participant will be listed and summarised by treatment using descriptive statistics.

Bioequivalence between MB05 and EU-Synagis®, between MB05 and US-Synagis® and between EU-Synagis® and US-Synagis® will be investigated for AUC0-inf and Cmax by analysis of variance using log-transformed PK parameter values. Bioequivalence will be assessed by calculating the 90% CIs for the ratio of the least squares geometric means for each pairwise comparison and each PK parameter. Bioequivalence will be concluded where the 90% CIs for the ratio of least squares geometric means are contained within the range 80.00% to 125.00%. For each pairwise treatment comparison and each PK parameter, this corresponds to undertaking two one-sided tests (TOST) of significance each at the 5% level.

Additional details of PK analysis will be provided in the study SAP.

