### 15.7 Bioequivalence Analysis

The bioequivalence analysis will be conducted for  $C_{max}$ , AUC0-inf and AUC0-last. Additionally, the bioequivalence analysis will also be conducted for concentrations collected on Days 29±1 day and 57±3 days as well as for partial AUC up to 168 hours, Days 29±1 day and 57±3. Natural log-transformed PK parameter  $C_{max}$ , C29days, C57days, AUC0-last and AUC0-inf, AUC0-168h, and AUC up to Days 29 and 57 will be analysed using the general linear model with the treatment as fixed via PROC GLM in SAS. For the purpose of the analysis, a preliminary ANCOVA model including variables group, age, sex, BMI and weight will be performed. If variables age, sex, BMI or weight were to be significant in this analysis, these variables will be kept in the final analysis. Upon review of the immunogenicity analysis, secondary ANCOVA analysis including ADA as a categorical or numerical variable could be performed. The 90% confidence intervals of the geometric least square mean ratio of test and reference i.e., MB05 group means relative to the EU-Synagis group means will be obtained by back transformation.

The following comparisons will be done:

(1) MB05 as Test VS EU-Synagis® as Reference

(2) MB05 as Test VS US-Synagis® as Reference

(3) EU-Synagis® as Test VS US-Synagis® as Reference

Bioequivalence will be concluded for  $C_{max}$ ,  $AUC_{0-last}$ ,  $AUC_{0-inf}$  and additional parameters  $C_{29days}$ ,  $C_{57days}$  and partial areas  $AUC_{0-168h}$ ,  $AUC_{29days}$  and  $AUC_{57days}$  between test and refere, if the 90% CIs for the ratio of geometric least squares means are contained within the range 80.00% to 125.00%. However, for  $C_{max}$ , a wider range 70.00% to 143.00% could also be considered.

Protocol Number: MB05-A-01-21 Document Status: Final 2.0 Version date: 15-Jun-2023

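### The 85% power in SAP 3 is for one comparison on one parameter; at the same inputs the power to match both EU- and US-Synagis is at most about 75%

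*SAP*

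**What the plan says.** SAP 3 takes "alpha of 0.05 (i.e., utilising a two-sided 90% CI around the mean difference"), states "Based on a worst-case CV of 0.35" and "a true hypothesised ratio for the mean difference of 1", and concludes that 45 per arm (135 in total) "will provide approximately 85% power to demonstrate bioequivalence of MB05 with EU-sourced Synagis® and US-sourced Synagis". A 5% dropout allowance brings enrolment to 47 per arm (141). The CV is the top of a stated range: "The reported coefficients of variation (CVs) for AUC and Cmax for Synagis® vary between 0.25 and 0.35". Section 3 gives no equivalence limits and does not say whether the power refers to AUC0-inf, Cmax or both.

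The primary objective in SAP 2.2.1 is "To establish the bioequivalence between MB05 and EU-Synagis®, between MB05 and US-Synagis® and between EU-Synagis® and US-Synagis® up to Day 99, in terms of" AUC0-inf and Cmax. Protocol 5.1 has the same objective.

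The testing is framed singly in Protocol 13.6.2: "For each pairwise treatment comparison and each PK parameter, this corresponds to undertaking two one-sided tests (TOST) of significance each at the 5% level". SAP 15.7 lists the three comparisons and sets 80.00–125.00% limits, but adds that for Cmax "a wider range 70.00% to 143.00% could also be considered".

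Neither document states a study-level success rule or a power for passing more than one comparison.

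**The concern.** The sentence in SAP 3 names two references joined by 'and', with no 'each' or 'per comparison'. Its plain reading is a single probability that MB05 is shown equivalent to both. Passing two tests is less likely than passing one, so a single-test figure overstates that probability unless the tests are almost perfectly correlated. They are not: the two comparisons share the MB05 arm but have different reference arms.

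What is at stake is the sponsor's view of risk. At the CV on which the trial was sized, the chance of missing at least one MB05 comparison would be taken as 15% when it is about 25% or more.

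**Working it through.** **Inputs.** From SAP 3: n = 45 per arm, CV = 0.35, true ratio 1 for MB05 against each reference (so EU against US is also 1), two-sided 90% CI. From SAP 15.7: limits 0.80 and 1.25, because SAP 3 states none, and a model with treatment only.

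**Step 1: reproduce the stated figure.**
- Log-scale SD: σ = √ln(1 + CV²) = √ln(1.1225) = 0.340.
- Standard error of a difference between two arms: σ√(2/n) = 0.340 × √(2/45) = 0.0717.
- Distance to either limit: ln 1.25 = 0.2231, which is 0.2231 / 0.0717 = 3.11 standard errors.
- Normal approximation: power = 2Φ(3.11 − 1.645) − 1 = 2Φ(1.47) − 1 ≈ 0.858.
- Exact TOST power: 0.852 with 88 degrees of freedom, 0.854 with the three-arm pooled variance (132 degrees of freedom).

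The stated 85% is therefore the power for one pair and one parameter.

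**Step 2: joint power, one parameter.** The differences MB05 − EU and MB05 − US share the MB05 mean. Their correlation is (σ²/n) / (2σ²/n) = 0.5. If they were independent, the joint power would be 0.852² ≈ 0.725; the correlation raises this a little. Simulation of the three arms, requiring the 90% CI to lie within the limits for every pair tested, gives:

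| One parameter, CV 0.35, ratio 1 | 45 per arm | 47 per arm |
|---|---|---|
| One pair | 85% | 87% |
| MB05 vs EU and vs US | 75% | 78% |
| All three pairs | 69% | 72% |

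At 45 per arm, separate and pooled variances give 74.7% and 75.1% for MB05 against both references, and 68.2% and 68.8% for all three pairs. The choice hardly matters.

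**Step 3: two parameters.** AUC0-inf and Cmax must both pass on 80.00–125.00%, with 45 per arm and CV 0.35 for both. The documents give no AUC–Cmax correlation, so a log-scale range is assumed:

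| Assumed correlation | MB05 vs both (4 tests) | All pairs (6 tests) |
|---|---|---|
| 0.3 | 57% | 48% |
| 0.7 | 62% | 54% |
| 0.9 | 67% | 60% |

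If Cmax is judged on 70.00–143.00%, a single Cmax test has power 0.999 and almost never fails. The results return to the one-parameter values, 75% and 69%. The wider range cannot lift them further, because AUC0-inf must still pass on 80.00–125.00%.

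**Step 4: sensitivity to the CV** (45 per arm, 80.00–125.00% limits; two-parameter figures at an assumed correlation of 0.7):

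| CV | One parameter, MB05 vs both | Two parameters, MB05 vs both | Two parameters, all pairs |
|---|---|---|---|
| 0.35 | 75% | 62% | 54% |
| 0.30 | 90% | 85% | 80% |
| 0.25 | 98% | 97% | 96% |

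**Step 5: what 85% on both references would take.** For one parameter at CV 0.35, about 53 to 54 evaluable per arm.

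**The case against.** **The 'and' may be distributive.** On that reading the sentence means 85% for each reference, and the arithmetic is right. Protocol 13.6.2 does frame the tests per pair and per parameter, and with no success rule stated, joint power is one possible target among others. It stands that the 85% is a correct number for something. But SAP 3 does not say for what, and the primary objective joins the pairs in the same way. The figure needs a label on either reading.

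**The 75% assumes no covariate adjustment.** SAP 15.7 keeps age, sex, BMI or weight in the model if they are significant, and the protocol stratifies randomisation by weight and sex. A residual CV of about 0.32 would give about 85% against both references on one parameter. That is a cut in log-scale variance from ln(1.1225) = 0.1156 to ln(1.1024) = 0.0975, or about 16%. This is possible, but the documents give no figure for it, and the stated 85% reproduces without any such gain.

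**CV 0.35 is the worst case.** True, and the shortfall is small or absent at 0.30 and 0.25. SAP 3 nevertheless ties its 85% to 0.35. The two-parameter figures also rest on an assumed correlation and are illustrative; the 75% does not.

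**Protocol 13.1 has a similar sentence.** It claims about 85% with 47 per arm at a true ratio of 0.95, where one comparison gives only about 77%. That is a separate discrepancy. It does not remove this one, but the two sections should be reconciled together.

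**Conclusion.** The concern holds. The 85% in SAP 3 is the power of one comparison on one parameter, and it is presented as the power to match both references. At the SAP's own inputs the joint figure is at most about 75%, some 10 percentage points lower. If the primary objective is read as needing all three pairs, it is at most about 69%, some 16 points lower. These ceilings rest on CV 0.35, ratio 1, 45 per arm, 80.00–125.00% limits for at least AUC0-inf, and no variance reduction from covariates. The planned confidence intervals and the type I error of each test are untouched. The consequence is confined to how the planning power is read.

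**What to change.** 1. In SAP 3, state that 85% is per comparison and per parameter. Add a short table of joint power for MB05 against both references, and for all three pairs if that is the success criterion, at CV 0.25, 0.30 and 0.35. Give the assumed AUC–Cmax correlation and the Cmax limits used.
2. In SAP 15.7, state which pairs and parameters decide the primary conclusion, in line with the two parameters in SAP 2.2.1. Label AUC0-last, C29days, C57days and the partial AUCs as supportive. The success rule and the Cmax range are for the sponsor to state.

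The cost is SAP wording and one power table, and the worst-case figure will look less favourable. No participants are added and the analysis does not change.

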## 4 STATISTICAL CONSIDERATIONS

#### 4.1 Standard Operating Procedures and Software

Data will be handled and processed per the sponsor representative's (Avance) Standard Operating Procedures (SOPs), which are written based on the principles of Good Clinical Practice (GCP).

All data conversions and statistical analyses will be performed using SAS® Version 9.4 or higher (SAS Institute, Cary, North Carolina, USA) with program code prepared specifically for the study by qualified Avance statisticians and SAS® programmers.

### 4.2 General Considerations

All data collected during the study (data originating from the electronic Case Report Forms (eCRFs) or electronic transfers will be presented in the data listings. Event-based listings will be sorted by treatment arm, participant identification and event start date/time (i.e., AE start date/time). Assessment-based listings will be sorted by treatment arm, parameter name (alphabetically unless specifically stated otherwise), participant identification, visit and time point (if applicable).

Unless otherwise stated, the following methods will be applied:

• Continuous variables: Descriptive statistics will include the number of non-missing values (n), arithmetic mean, standard deviation (SD), median, minimum, and maximum values.

The minimum and maximum values will be displayed to the same decimal precision as the source data, the arithmetic mean and median values will be displayed to one more decimal than the source data, and the SD values will be displayed to two more decimals than the source data for the specific variable.

The appropriate precision for derived variables will be determined based on the precision of the data on which the derivations are based, and statistics will be presented in accordance with the abovementioned rules.

- Categorical variables: Descriptive statistics will include frequencies and percentages per category. The denominator in all percentage calculations will be the number of Participants in the relevant analysis population with non-missing data, unless specifically stated otherwise. Percentages will be rounded to one decimal place and will not be displayed for zero frequencies.
- Presentation of p-values and confidence intervals: 90% confidence intervals will be computed, and reported to four significant figures, p-values will be displayed up to three decimal places and as "<0.001" if the value is below 0.001.
- Repeat/unscheduled assessments: Only values collected at scheduled study visits/time points will be presented in summary tables. If a repeat assessment was performed, the result from the original assessment will be presented as the result at the specific visit/time point. All collected data will be included in the data listings. If an unscheduled visit was intended to replace the missing assessment for a scheduled visit this should be documented clearly before values are carried forward as a scheduled visit assessment.
- Assessment windows: All assessments will be included in the data listings and the protocol specified visit windows will not be applied to exclude assessments that were

not performed on the protocol specified visit days. Protocol visit windows will be as per CRF data collection.

- Result display convention: Results will be centre aligned in all summary tables and listings. Participant identification, visit, and parameter labels and comments may be left aligned if required.
- Conversion of categorical values: In some instance, continuous variables may be expressed as a range (i.e., < 9). The original source data captured will be displayed in data listing (i.e., <9), while values may be converted to another number for summary table purposes and the calculation of change from baseline values. As an example, a value of < 9 may be converted to one significant figure less as 8.
- Date and time display conventions: The following display conventions will be applied in all outputs where dates and/or times are displayed:
  - Date only: YYYY-MM-DD
  - o Date and time: YYYY-MM-DD/HH:MM

If only partial information is available, unknown components of the date or time will be presented as UN (Unknown), for example "2022-UN-UN" or "UN:UN" for time.

